1 INTRODUCTION

Inadequate management of preoperative mental health disorders often contributes to poor postoperative outcomes [1], including increased rates of readmission, delirium, falls, and mortality [2-5]. However, very little work has been done to improve perioperative mental health. In particular, there have not been any systematic efforts to identify evidence-based behavioral interventions that were originally developed for depression and anxiety in otherwise medically well psychiatric patients, adapt them for use in surgical populations, test their effectiveness in these patient populations, and study implementation strategies.

The proposed study will focus on comparing a perioperative mental health intervention of behavioral therapy focused on Behavioral Activation (BA), plus Medication Optimization (MO), compared to enhanced usual care, among older adults undergoing cardiac, orthopedic or oncologic procedures with anesthesia (N=300; n=100 each surgical type). We chose to use enhanced usual care to provide some harmonization between the participants in the usual care arm. Providing resources to participants in both arms increases the possibility of benefit for all participants, which may potentially improve recruitment and retention.

We hypothesize that the mental health intervention can mitigate anxiety and depression symptoms during the perioperative period [6]. Towards this end, we propose to test the effectiveness as well as the implementation potential of the intervention in a Hybrid Type 1 Effectiveness-Implementation RCT Design.

This study includes adults aged 60 and older with current depression/anxiety symptoms (PHQ-ADS ≥ 10) and that are undergoing major orthopedic, cardiac or oncologic procedures. Each patient is randomized to the perioperative mental health intervention vs enhanced usual care.

|

2 ANALYSIS OBJECTIVES

Aim 1. Examine the effects of a perioperative mental health intervention, composed of a wellness program and medication optimization, on depression/anxiety symptoms compared to enhanced usual care in patients undergoing a scheduled cardiac, orthopedic or oncologic surgical procedure.

H1: A greater decrease in depression/anxiety symptoms will occur in patients randomized to the perioperative mental health intervention compared to patients randomized to enhanced usual care.

3 ANALYSIS SETS/ POPULATIONS/SUBGROUPS

We will randomize older adults aged ≥ 60 to either the perioperative mental health intervention or enhanced usual care. The modified intent-to-treat analyses will include all patients that underwent a orthopedic, cardiac or oncologic surgical procedure. The goal target in the mITT group is 300 patients, with approximately 100 patients in each surgical cohort. Patients can choose to refuse any component of this study.

4 DATA SOURCE

Below is a schedule of the primary outcome measures

Effectiveness Outcomes		Data Source	Description	Data Collection Mechanism	Time points
Primary (Clinical)	3-month change in anxiety and/or depression symptoms	PHQ-ADS [7]	A validated composite of symptoms of depression and anxiety	Patient self-report	Baseline; 1mo and 3 mo

Note. PHQ-ADS = Patient Health Questionnaire Anxiety and Depression Scale;

5 RANDOMIZATION

All eligible and consented participants will be randomized in a 1:1 ratio to receive either the perioperative mental health intervention or enhanced usual care. The study biostatistician generates the randomization table using a variable block sequence. The assignment of the treatment condition for each individual participant will be done by the REDCap® randomization module [15,16] after confirming trial eligibility. For participants assigned to the intervention, a randomization table will be generated using a similar block sequence design, and the data manager will manually select the individual intervention team member according to the randomization table and record that information in REDCap®. This process will trigger an automatic notification via REDCap® to the assigned interventionists.

6 BLINDING

Research coordinators responsible for collecting outcome data throughout the study will be blinded until data collection is complete. At the end of the 3-month follow-up, the research coordinators will complete a blinding question to guess the arm to which each participant was allocated. This will allow the team to determine the effectiveness of the blinding procedures [17]. Upon completing this form, it will be locked by the data manager, and the participant's assignment will be revealed to the research coordinators to conduct the end-of-study interviews with the participants in the intervention arm.

7 MINIMIZATION OF BIAS

Enrollment will not be based on sex or ethnic background. Standard Care will not be affected for any of the patients due to study participation. Completion of the outcomes will be entirely patient-reported, to minimize the assessor's bias in interpreting patient responses.

8 ENDPOINTS AND COVARIATES

Primary outcome

The primary outcome of the study is the change in PHQ-ADS from baseline to 3-month visit. All models will be adjusted for covariates which strongly associate with the outcome and which may differ across patient sub-populations.

9 HANDLING OF MISSING VALUES AND OTHER DATA CONVENTIONS

The data is regularly reviewed to identify missing data. All models will be fit with SAS or R using a maximum likelihood criteria which utilizes all available information yielding optimal solutions in the face of missing data as long as it is missing at random. Multiple imputation will be used where the statistical model does not already provide appropriate protection for data missing at random.

- For the clinical assessments, if the scale consisted of 6-10 items and a participant is missing one item, then the average of the other items will be used to fill in the missing item. If more than 1 item is missing, then that participant's data will not be used for that scale. For a 1-5 item scale, any missing data will exclude that participant's data for that scale. For scales with greater than 10 items, a 10% cutoff rule will be employed for missing data.

10 STATISTICAL PROCEDURES

[figure not shown]
10.1 Primary Outcome Analyses

The primary outcome of the study is the change in PHQ-ADS from baseline to 3-month visit. In each surgical cohort, a mixed model repeated measures ANOVA with a treatment group by time point design will be run to determine the overall impact of the intervention on the change in the PHQ-ADS. The results will be synthesized using a prespecified fixed-effects meta-analysis of the three trials, and the plan is for this to be the primary analytic strategy to demonstrate effectiveness of the intervention across all surgical subgroups. The mixed model within each cohort is ideal because it uses all available data and is robust despite missing data. The population used for the primary analysis is a modified Intent to Treat (mITT) group consisting of those randomized participants who actually undergo the surgery (ie, for randomized participants in whom the surgery is cancelled or indefinitely delayed, they are not part of the analysis sample). Participants will still be included in the analysis if they died post-operatively or were lost to followup, prior to the end of the trial. Statistical significance will be set at 0.05 and relevant changes in PHQ-ADS will be estimated along with 95% confidence intervals. Any data available at baseline, 1 month or 3 months are included in the repeated measures model. The three-month response is the primary outcome and is tested with an appropriate contrast to compare the change between the two groups from baseline to 3 months.

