10.2 Power

We based sample size on the need to have adequate power to examine intervention effects within each of the individual surgical subgroups ($n=100$ each), as well as the planned meta-analysis ($N=300$). To estimate the power, we examined the manuscript that provided the original validity and reliability studies for the PHQ-ADS [49] and one of the trials that provided data for that study (Stepped Care to Optimize Pain care Effectiveness (SCOPE)) [84,85]. The PHQ-ADS authors estimate the minimal clinically important difference (MCID) from the standard error of measure as 3-4 points [49]. Since the SCOPE trial was a pain relief study without a requirement for anxiety or depression, we conducted a blinded sample size reassessment after 125 participants had completed the 3-month assessment in the 3 cohorts. The average change in the PHQ-ADS was 6.7 with a standard deviation of 8.8 ($d= 0.76$). These 125 subjects were from 135 in the mITT group, or 7% dropout. With the chosen sample size of 50 mITT subjects in each group, we estimated the power for a simple t-test between the two groups of size 46, a 2-tailed significance level of 0.05, and a difference between the two groups of >4 points as shown in figure 1 below. These power calculations are somewhat conservative as they are based on a simple t-test and we will be using a repeated measures ANOVA for the actual analysis.

Figure 1: Power calculation curve suggesting a power of at least 55% for groups of size 46, calculated from a mITT sample size of 50 in each group with a 7% dropout, and a difference between groups >4 points.

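### The primary contrast subtracts baseline PHQ-ADS with a fixed weight of 1 instead of adjusting for it: valid, but precision is lost unless the follow-up-on-baseline slope is near 1

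*SAP*

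**What the plan says.** Section 10.1 defines the endpoint: "The primary outcome of the study is the change in PHQ-ADS from baseline to 3-month visit". Each surgical cohort gets a repeated-measures mixed model with treatment group and time point as factors, and a fixed-effects meta-analysis combines the three cohorts as the primary strategy. Baseline is one of the response occasions: "Any data available at baseline, 1 month or 3 months are included in the repeated measures model". The 3-month result is "tested with an appropriate contrast to compare the change between the two groups from baseline to 3 months". The analysis set is a modified intention-to-treat group "consisting of those randomized participants who actually undergo the surgery", and "Participants will still be included in the analysis if they died post-operatively or were lost to followup".

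Section 8 adds a general promise: "All models will be adjusted for covariates which strongly associate with the outcome and which may differ across patient sub-populations". It names no covariate.

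Section 10.2 bases power on a t-test of change with SD 8.8 and 46 per group, and comments: "These power calculations are somewhat conservative as they are based on a simple t-test and we will be using a repeated measures ANOVA".

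**The concern.** When baseline is a response, each arm has its own baseline mean and the contrast is a difference in change, every patient's baseline is subtracted with a weight of exactly 1. A baseline-adjusted analysis estimates that weight from the data. The two coincide only when the slope of the 3-month score on baseline is 1; otherwise the change-score comparison carries avoidable variance. Equivalently, each point of chance baseline imbalance moves the change-score estimate by 1 minus the slope.

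The unnamed covariates in section 8 do not settle this. Baseline PHQ-ADS is already a response in the model, and a covariate entered as a main effect largely cancels from a contrast of change over time. Only a baseline-by-time term, baseline moved out of the response, or a common baseline mean would alter the weight, and none is stated.

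The loss falls where the design is weakest. Section 10.2 says the sample size was meant to serve each cohort, yet claims only at least 55% power there. It also puts the minimal important difference at 3 to 4 points, so a pooled effect of 3 points is relevant too.

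**Working it through.** **Inputs from SAP section 10.2.** SD of change 8.8 (blinded, 125 completers); 46 per group per cohort; two-sided 5% level; difference 4 points (stated as more than 4); dropout 7%; minimal important difference 3 to 4 points. Pooled size is 3 × 46 = 138 per group, treated as one two-group comparison to approximate the meta-analysis.

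**Assumed, because the SAP does not give them.** The baseline-to-3-month correlation ρ, and k = follow-up SD / baseline SD. Section 1 sets entry at PHQ-ADS 10 or more, which truncates baseline but not follow-up, so k above 1 is plausible.

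**1. The plan's own figure.** SE = 8.8 × √(2/46) = 1.835 and 4/1.835 = 2.18. Noncentral-t power is 57.8%, consistent with the stated lower bound of 55%.

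**2. What the contrast does.** On a simulated complete data set, the group-by-time contrast equalled the difference in mean change exactly (−1.4977 both ways). Adding baseline as a main-effect covariate under compound symmetry left it at −1.4977. Constraining the arms to a common baseline mean gave the analysis-of-covariance estimate (−1.3280 both ways).

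**3. Formula.** Slope b = ρk. Var(change) = Var(follow-up given baseline) + (b − 1)² × Var(baseline), hence

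Var(adjusted)/Var(change) = k²(1 − ρ²) / (1 + k² − 2ρk).

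Example with k = 1, ρ = 0.5: 0.75/1 = 0.75, so the adjusted SD is 8.8 × √0.75 = 7.62, the SE is 1.589, 4/1.589 = 2.52, and power is 70.2%.

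**4. Results with change SD held at 8.8.**

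| k | ρ | slope | variance ratio | cohort power, 4 points (57.8% unadjusted) | pooled power, 3 points (80.6% unadjusted) |
|---|---|---|---|---|---|
| 1.0 | 0.3 | 0.30 | 0.650 | 76.3% | 93.8% |
| 1.0 | 0.5 | 0.50 | 0.750 | 70.2% | 90.3% |
| 1.0 | 0.7 | 0.70 | 0.850 | 64.8% | 86.4% |
| 1.2 | 0.3 | 0.36 | 0.762 | 69.5% | 89.8% |
| 1.2 | 0.5 | 0.60 | 0.871 | 63.7% | 85.6% |
| 1.2 | 0.7 | 0.84 | 0.966 | 59.2% | 81.9% |
| 1.4 | 0.3 | 0.42 | 0.841 | 65.2% | 86.8% |
| 1.4 | 0.5 | 0.70 | 0.942 | 60.3% | 82.8% |
| 1.4 | 0.7 | 0.98 | 1.000 | 57.8% | 80.6% |

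With k = 1 the SE falls by 19/13/8% for ρ = 0.3/0.5/0.7. Pooled power at 4 points is 96.4% unadjusted and 99.7/99.1/98.3% adjusted.

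**5. Simulation (20,000 trials per setting, 46 per arm).** With k = 1, power was 57.8/58.1/57.7% for the change score and 76.1/70.3/64.2% adjusted. Type I error, checked at slopes 0.5 and 1, was 4.9 to 5.0% for both methods, and both were unbiased. At slope 1, power was 58.2% for the change score and 57.6% adjusted: adjustment then costs about one degree of freedom.

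**6. Does the repeated-measures model itself add power?** Assume 50 per arm, 7% missing at 3 months (half of those with a 1-month score), equal correlations and k = 1. The variance of the treatment difference, with normal-approximation power, is:

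- t-test: 2 × 8.8²/46.5 = 3.33; 59.2%.
- Model as written, ρ = 0.3/0.5/0.7: 3.25/3.26/3.28; 60.3/60.0/59.8%.
- Baseline as covariate, or common baseline mean: 2.16/2.49/2.81; 77.7/71.8/66.4%.

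The model as written gains about 1 point.

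**7. Chance imbalance.** With k = 1, the baseline SD implied by a change SD of 8.8 is 7.44/8.80/11.36. With 50 per arm, one SE of imbalance is that SD × √(2/50) = 1.5/1.8/2.3 points. Multiplied by (1 − ρ), the change-score estimate shifts by 1.0/0.9/0.7 points. For unequal SDs the factor is 1 − ρk.

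**The case against.** The strongest reply is that nothing here is an error. The SAP declares change as the endpoint and tests change with a recognised, valid longitudinal model; that a more efficient model exists is close to preference. The primary strategy is the pooled analysis, which already has about 96% power at the planning difference. The gain rests on two quantities absent from the SAP, and equal SDs are the favourable end of the range shown. If truncation at entry halved the baseline variance and left the slope unchanged at 0.3/0.5/0.7, the variance would fall by only about 21/14/8% and cohort power would be 68/64/61%.

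Four smaller points also have some force. Chance imbalance is the same lost precision seen conditionally, not a second harm. A gain of 1 point arguably fits the modest claim in section 10.2. The SAP does not exclude a baseline-by-time term, so the weight of 1 is inferred partly from silence. And with baseline as a covariate, patients with only a baseline score no longer contribute.

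Most of this stands as a limit on size: the test is valid, the gain is uncertain, and the pooled result at 4 points barely moves. It does not remove the point. Section 10.2 itself makes the cohorts a basis for the sample size and includes 3 points in the important range. The natural reading of section 10.1 gives a weight of 1, and a SAP should state how baseline enters its primary model. The loss of baseline-only patients is already in step 6, where the adjusted variance is still clearly lower.

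**Conclusion.** The point holds as a matter of precision, not validity. As written, the primary contrast compares change scores. Over the assumed ranges (ρ 0.3 to 0.7, SD ratio 1 to 1.4, change SD 8.8), baseline adjustment would lower the variance by between 35% and essentially nothing, with the gain vanishing as the slope nears 1. The benefit is mainly for the cohort analyses and for a pooled difference of 3 points. The statement in section 10.2 that the t-test power is conservative has the right direction but little behind it under the model as written. The change is recommended rather than essential: at worst it costs about one degree of freedom. Confidence in the size is moderate, because the SAP does not report the slope.

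**What to change.** - **Section 10.1:** model the 1- and 3-month PHQ-ADS scores as responses, with treatment, time, treatment-by-time, baseline PHQ-ADS and baseline-by-time, and test the adjusted 3-month treatment difference. With baseline held as a covariate, this is the same treatment difference as the difference in change, so the endpoint is unchanged. The model does not need equal baseline means in an analysis set restricted after randomisation to patients who have surgery. A model with a common baseline mean is an alternative if equal baseline means are accepted in that set.
- **Section 10.1, inclusion sentence:** state that a patient with no score after baseline stays in the modified intention-to-treat count but adds no information to this contrast.
- **Section 8:** name baseline PHQ-ADS as a fixed adjustment.
- **Section 10.2:** rest the claim that the power is conservative on the baseline-adjusted model.

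The cost is SAP wording and a small change to the model statement. Baseline PHQ-ADS is already collected, the endpoint and time point stay the same, and no extra patients are needed. Make the change before unblinding, so that the handling of baseline is not chosen with results in view.

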10.2 Power

We based sample size on the need to have adequate power to examine intervention effects within each of the individual surgical subgroups ($n=100$ each), as well as the planned meta-analysis ($N=300$). To estimate the power, we examined the manuscript that provided the original validity and reliability studies for the PHQ-ADS [49] and one of the trials that provided data for that study (Stepped Care to Optimize Pain care Effectiveness (SCOPE)) [84,85]. The PHQ-ADS authors estimate the minimal clinically important difference (MCID) from the standard error of measure as 3-4 points [49]. Since the SCOPE trial was a pain relief study without a requirement for anxiety or depression, we conducted a blinded sample size reassessment after 125 participants had completed the 3-month assessment in the 3 cohorts. The average change in the PHQ-ADS was 6.7 with a standard deviation of 8.8 ($d= 0.76$). These 125 subjects were from 135 in the mITT group, or 7% dropout. With the chosen sample size of 50 mITT subjects in each group, we estimated the power for a simple t-test between the two groups of size 46, a 2-tailed significance level of 0.05, and a difference between the two groups of >4 points as shown in figure 1 below. These power calculations are somewhat conservative as they are based on a simple t-test and we will be using a repeated measures ANOVA for the actual analysis.

Figure 1: Power calculation curve suggesting a power of at least 55% for groups of size 46, calculated from a mITT sample size of 50 in each group with a 7% dropout, and a difference between groups >4 points.

11 QUALITY CONTROL PLANS

Data quality will be assessed using REDCap validation methods and ongoing review of data (e.g., identification of missing data, outliers, etc.). Range and consistency checks will also be employed.

12 PROGRAMMING PLANS

Statistical software (SAS and R) will be used to produce results and raw data will be available for accompanying papers to be submitted for publication (following approval by Principal Investigators).

13 FUNDING AND ACKNOWLEDGMENTS

This research is supported by a grant from the National Institute of Mental Health (P50MH122351), which established the Center for Perioperative Mental Health at Washington University.

